#### **3.2.B. Protection Against Risk.**

Although we are working with participants who have been convicted of DWI and mandated to treatment, their participation in this research study has absolutely no bearing on the requirements they need to fulfill obligations with the court. To minimize the risk of coercion to participate, we will make it clear both verbally and in the consent form that participation in the study will not help nor hinder their standing with the courts. Although participants in this study are not prisoners, they are involved in the criminal justice system insofar as they have been convicted for DWI. We will make it very plain that data collected as part of the research study will not be available to the courts and will have no bearing on their DWI status with the courts. Because they are not prisoners they will not require special protections, but we still need to be mindful that simply being involved in the criminal justice system makes them more vulnerable than a group not involved in the criminal justice system.

To minimize potential psychological risk, all focus group and usability testing facilitators will establish ground rules for discussion that includes an open, non-evaluative exchange of comments and ideas. All surveys and data collection forms will be approved by an IRB and employed under the supervision of senior project staff. Participants will be told that they do not have to answer any questions which make them uncomfortable and can terminate their participation at any time they wish.

Notes, surveys, audiotapes, and data will be accessible only by research personnel. No clinical data will be

captured. The data collected on this project will be obtained with the "use of educational tests, survey questions, [and] interview procedures."

Data forms will be labeled only with participant identification number. Participant names and study identification numbers will be recorded and stored separately from the research data files. Focus group participants will be asked to use first names only during focus groups. Data will be de-identified before being submitted for analysis. All notes and printed data collection forms and questionnaires will be stored in locked cabinets; all electronic data files will be stored on UNM's and/or KB's secure network servers behind computer firewalls, with routine backup. All identifiers will be stored in secure files and behind computer firewalls and results will be shared in aggregate form only. All human subjects participating in this project will be adults who are 18 years and older.

All focus group and usability testing research data collected by research staff (e.g., focus groups scales, demographic and locator forms, etc.) will be logged in and taken back to the CASAA research offices in a briefcase or similar closed storage medium for transport - loose papers or papers in open folders will not be allowed. After returning to the research office, all hard copy materials (consent forms, demographic and locator forms, usability scales) will be logged in and stored in a locked file cabinet, within a locked office, in a locked suite. Once information from the focus groups is transcribed, the transcriptions will also be placed within the locked file cabinet. There is a risk that data could be accessed by someone other than project staff. While hard copies of materials will be placed within a locked filing cabinet, inside a locked office, digital audio recordings will be uploaded to a secure server located within UNM-CASAA and transcribed. The UNM-CASAA server is located in a locked room, on the second floor of the CASAA building, which is burglar alarmed. Access to the server in the locked room is gained through the IT Manager's office. Only four staff members (having a need to have access to the server) have keys to that locked room. Electronic access to files and data are provided by the IT Manager on a need to know basis, meaning staff can only access that part of the server on which their project-specific files and data reside. The server is protected by IT protocols and a firewall from outside access and attacks. The only outside access is through a secure virtual private network (VPN). The VPN requires a shared key that is known only by the IT manager. The original focus group digital audio recordings will be deleted from the recording device once the recording is uploaded to the previously mentioned server.

To minimize the risk to participant data privacy and protection through the internet in the randomized trial, KB programmers will monitor and maintain all programs and databases and use an established protocol for participant cyber safety and security. KB is HIPAA compliant and maintains vigorous technical safeguards which are built into KB's IT system to protect information and to control access to it. All participant information will be protected using 128-bit SSL encryption. All Internet information must travel through KB's CISCO ASA 5505 firewall using ASA software version 9.0(2) encrypted 3DES-AES. Traffic then moves to KB's web server. This server is a Dell Power Edge T-310 with 32 GB of RAM, 1.5 TB available disk space on a RAID 5 redundant drive system using Windows Hyper-V Operating System. The virtual web server uses Windows 2008 IIS Web server software. User click stream data is collected using Webtrends and is saved to our SQL server. Enrollment data is transferred to our SQL server (Windows Server 2008) which uses MS SQL server 2008 R2 database software. This machine is also a Dell Power Edge T-310 with 32 GB of RAM, 1.5 TB available disk space on a RAID 5 redundant drive system using Windows Hyper-V OS and has no access to the Internet. When a participant is directed to take a survey, their computer is linked to a third server in our system which is also a Dell Power Edge T-310 with 32 GB of RAM, 1.5 TB available disk space on a RAID 5 redundant drive system using Windows Hyper-V OS. This server runs Question Pro Survey software. Data from each survey is collected and saved to the SQL server mentioned above. All network traffic is sent from the CISCO firewall to a Syslog server using Manage Engine Firewall Analyzer 7 software. Login and network activity is required and monitored by Windows servers to an event viewer. Servers are kept in a locked room on site. All files are secured locally using MS NTFS. All traffic between servers and PCs on the LAN are digitally signed communications. Each local machine has a built-in operating system firewall. Data from the Question Pro surveys are exported for data analysis by local machines which are also behind KB's firewall. Access to this exported data by outside sources is done using File Transfer Protocol (FTP) protected by Secure Socket Layer (SSL). SQL databases are protected by the built-in security of MS Active Directory. Data is backed up using a Quantum SuperLoader 3 tape library using LTO4 tapes that contain 800 GB/1.6 TB of info (depending on compression used). The device holds 16 tapes. The backup software used by KB is Symantec Back-up Exec. 2012. Daily backups are incremental and tapes are recycled weekly. Weekly backups are done every Friday and are recycled every 6 weeks. Monthly backups are done on the last Friday of each month and are full backups of all data. These monthly tapes are stored in a secure offsite facility and are never recycled.

With regards to app security on personal devices, Apple (e.g., iOS programmed apps) completes a full security review of any app installed on a phone including beta/testing apps through their App Transport Security (ATS). KB App programming will include all key developer-related features to ensure ATS security. Google Play (Android programming) does not conduct a similar security check; however, KB has extensive experience with developing and marketing both iOS and Android programmed apps using an established

protocol (SSL/TLS: Secure Sockets Layer/Transport Security Layer) and has never experienced a data breach. All usability testers will be informed that information being sent to and from their device will remain encrypted and password protected, and at any time they are allowed to opt-out and uninstall the app.

### **3.3. POTENTIAL BENEFITS OF THE PROPOSED RESEARCH TO PARTICIPANTS AND OTHERS**

Potential benefits for all participants will be the knowledge that one has helped in development of an innovative method of maintaining the cessation of intoxicated driving. Participants may benefit by knowing that they are instrumental in developing the content that will help others.

A description of this study will be available on <http://www.ClinicalTrials.gov>, as required by U.S. Law. This website will not include information that can identify the participant. At most, the website will include a summary of the results. This website can be searched at any time.

### **3.4. IMPORTANCE OF THE KNOWLEDGE TO BE GAINED**

We are proposing two innovations with potential to enhance maintenance of changes in drinking that begin with the DWI conviction and installation of the IID by extending the reach of treatment into the offender's world through family-involved treatment and smartphone technology to reinforce treatment interventions. We believe these interventions have the potential to provide efficient means to decrease an important public health consequence of risky drinking and will add substantial original knowledge to the DWI field.

This study will be the first to use smartphone technology to extend and make permanent the cessation of intoxicated driving, providing an intervention that uses easily-accessible and diffusible technology.

### **3.3. DATA AND SAFETY MONITORING PLAN**

A data safety and monitoring plan will be implemented for this project, following well-established procedures within KB and UNM. We will not set up an independent Data Safety and Monitoring Board because this trial is very low risk; does not include use of therapeutics; and physical risks are not anticipated. The progress of the research will be monitored monthly by the PI, Co-Investigators, Project Coordinator, and Project Biostatistician, who will meet bi-weekly to discuss the activities in the project, participant recruitment, and data collection. Any issues that the research scientist has identified will also be discussed at that time.

The study investigators have extensive experience in clinical trials organization and management, including data safety monitoring for single site and multisite trials. Relevant study staff will also be trained in monitoring and documenting adverse events.

Critical events will be reviewed by the investigators to ensure that project methods have not been intrusive or disruptive. Annual reports on data safety and monitoring are submitted to the IRBs. Compliance with data collection protocols will be monitored throughout data collection by the Investigators and Project Coordinator. The data management staff at KB will examine the quality of data input throughout the data collection period following standard quality control and assurance procedures (e.g., double entry of hard-copy coded data; detection and estimates of keystroke errors, identification of systematic mistakes in coding or responses; range checks). Analyses of the data will be performed by [name] and [name] at the conclusion of the data collection period to assess distributional assumptions and the success of randomization. By having the Project Coordinator, Project Biostatistician and data management staff monitor the data, the PI's conflict of interest is reduced. The PI and Project Coordinator are responsible for reporting all adverse events to the IRBs. Only Grade 1 events are expected on this trial. Thus, adverse events will be reported annually, as required by DHHS. This report will be reviewed by the IRBs. Any action taken by the IRB or project investigators resulting in a temporary or permanent suspension of the trial will be communicated immediately by the PI to the NIH program officer.

All study staff will be required to report serious adverse events within 24 hours of their occurrence, regardless of their relevance to the study. The PI will be required to provide a report of all serious adverse events to the IRB within 24 hours of the reporting.

An annual report will be submitted to the IRB. This report will include all progress report categories.

The governance structure for the research team is designed to take advantage of the expertise of each investigator, consultant, and staff person, while minimizing overlap. The PI, [name], is responsible for governance of the overall study and he will chair a Steering Committee comprised of the Co-Investigators (Drs. [name], [name], and [name] and [name]), Biostatistical Advisor ([name]), and Project Coordinator. The Steering Committee will communicate with NIH and IRBs. This Committee will meet weekly to make design and administration decisions, plan activities, track progress across sites, trouble-shoot problems, maintain consistency in actions, and implement quality controls. Major decisions concerning the project will be made within the Steering Committee with the ultimate decision-making responsibility residing with [name].

Four subcommittees will supervise important parts of the project. [name] will chair the Recruitment Committee that will recruit the participating DWI Offenders and CFMs. [name] will be on this committee. Drs. [name] and [name] will co-chair the Intervention Development Committee and will be assisted by [name], [name], and the KB media developers. Drs. [name] and [name] will Co-Chair the Data Collection Committee and survey the DWI Offenders and CFMs and obtain the cumulative IID lockout event data for the DWI offenders from the Santa Fe County DWI Program at the 9-month assessment point. [name], Project Biostatistician, will assist in the development of the procedures for the surveys and lockout event collection. This committee will work to ensure that all data collection procedures have detailed protocols. The Analysis Subcommittee, co-chaired by [name] and [name] with Drs. [name], [name], and [name] and [name] as members, will plan and conduct all data management and analysis procedures. This subcommittee will develop a detailed data analysis plan and supervise work by KB's Biostatistical Manager to prepare all databases for analysis. The subcommittees will meet on a weekly, biweekly or monthly basis as needed depending on the project tasks and activities. Ad hoc committees will be formed to address specialized tasks as necessary. [name] will supervise project activities at KB; [name] will supervise project activities at UNM; and [name] will supervise project activities at Pythagoras, Inc.

The Project Coordinator at KB, [name], will assist [name] with all aspects of the project. [name] will coordinate the relationships among the investigators and project staff, sit on the Steering Committee, and oversee the conduct of the study protocols. [name] (Biostatistical Manager) and [name] (Data Assistant) will perform data management and [name] will assist [name] with day-to-day data analysis tasks. [name] and [name] will create data entry programs for printed forms. [name] and [name] will work with the IRBs to obtain approval of all forms and procedures. [name], [name], and [name] will work together to ensure successful transfer of database files and performance of all analyses.

With investigators collaborating from two organizations, high quality communication among project staff and investigators will be maintained by using telephone, fax, email, web-assisted conference call technology, and Wrike, KB's new, robust, real-time, cloud-based work management software. We successfully conducted the Phase I research on the *B-SMART mobile web app* with investigators from these same institutions and [name] has successfully conducted other multi-institution trials using these same communication methods. Regular meetings of the Steering Committee and subcommittees will take place using telephone and web conferencing technology. All investigators and staff will meet in person at KB three times each project year. Telephone and email will be used for day-to-day communication, as needed. With Wrike, the team is able to organize the important components of a project and break large deliverables into manageable pieces, attach files, communicate quickly, and assign tasks with due dates. It allows for live editing and file management to facilitate efficient collaboration amongst users. KB staff are equipped with full licenses to use all features of Wrike and investigators outside of KB will be provided with a collaborator license. Having project-related files, deliverables, and tasks in a centralized location greatly improves communication among investigators and research staff. Wrike practices industry-standard network protection procedures, including network segregation, firewall and router technologies, intrusion detection systems, log aggression and alert mechanisms. TLS technology protects information accessed in Wrike using both server authentication and data encryption. This is equivalent to network security methods used in banking and leading e-commerce sites. KB's IT manager oversees Wrike security and activity.

Conflicts will be handled through frank discussions within the Steering Committee and subcommittees. All sides of an issue or sources of the conflict will be discussed and a final decision will be rendered through group consensus when possible. Conflict arising from differences in interpersonal style will be handled by the PI, respecting the privacy of those involved. If conflict cannot be resolved within the research team, [name], a Senior Scientist at KB who is a clinical psychologist and not a member of the research team, will serve as an outside mediator, meeting with both sides in the dispute and recommending ways to resolve it. If the conflict still cannot be resolved, a mediator from Mountain States Employer Council will be hired to mediate the dispute. This Council provides business advice and services to small businesses. KB has been a member of this Council for 11 years and regularly uses its business services. At that point, the research team will agree to make the mediator's decision binding. We have used these same management procedures to conduct successfully community-based research in previous multi-institutional projects.

Behavioral (e.g., Psychotherapy, Lifestyle Counseling)	B-SMART Mobile Web App	The B-SMART mobile web app will contain four modules: 1) Supporting Abstinence, 2) Shared Positive Activities, 3) Common Challenges for Family Members with IID, and 4) Effective Communication. Within each module there will be a series of learning activities, including presentation text, interactive engagement, and videos. All app content will be available in both English and Spanish, based on user language preference.
Behavioral (e.g., Psychotherapy, Lifestyle Counseling)	Usual and Customary Ignition Interlock Device Information	Participants randomized to the usual and customary care (UC) group will receive a website with a pamphlet on the IID installed in their vehicle and the manufacturer information provided about the IID in PDF format, in both English and Spanish. This constitutes a UC group, as such pamphlets are widely available to DWI offenders who have IIDs installed in their vehicles. Thus, providing this pamphlet represents a standard information provision for first-time DWI offenders and their CFMs.

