### 3C.6. Randomized Trial Evaluating *B-SMART* (Specific Aim 4; Months 8-24)

**3C.6.1. Experimental Design.** The *B-SMART mobile web app* will be evaluated in a randomized pretest-posttest controlled design. In months 6-11, first time DWI offenders and CFMs will be recruited for participation in the trial. First-time DWI offenders and their CFMs will be randomized together to the intervention (*B-SMART*)

(n=150) or a usual and customary (UC) IID information condition comparison group (n=150) following baseline assessment. Assessment via web-based surveys will be conducted with the DWI offenders and CFMs at baseline, 3-month follow-up, and 9-month follow-up

post randomization. Also, information on frequency of alcohol-positive IID tests (termed “lockout events”) will be acquired by the project from the Santa Fe County and Municipal DWI Program at the 9-month assessment point (posttest only) for each DWI offender. Thus, the proposed efficacy trial (see **Figure 5**) will be a 2 (level of treatment – app intervention vs. UC information) x 3 (level of time – baseline vs. 3-month follow-up vs. 9-month follow-up) mixed factorial design. Baseline and follow-up data collection will be conducted via online surveys and a customized web portal and include DWI offender and CFM alcohol frequency and use measures and measures of family communication and functioning (see 3C.7). Participants will fill out a locator form with contact information and collateral contact information to locate them for assessment at the 3-month and 9-month follow-ups. We have employed these locator procedures in prior trials, keeping average loss across 9 months at 15%-20%. Cumulative IID lockout event data will be collected for all DWI offenders from the Santa Fe County DWI Program at the 9-month assessment point.

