**Study Materials:** Data from the focus groups, usability testing, surveys, and randomized trial will be collected in the form of handwritten notes, audio tapes, computer files, transcriptions, and questionnaires. Discussions will be recorded, transcribed, and analyzed using *Atlas.ti*® software. Data will be gathered from surveys used in the randomized trial. Data will be obtained specifically for research purposes and will be kept confidential with access limited to the Investigators and specific project staff. All data will be kept in locked files.

**Potential Risks:** Potential risks are minimal, mainly social or psychological. Focus group participants may be hesitant or uncomfortable responding to questions about the challenges of having an IID, concerns about family members' feelings about the IID, and ways that family members could be helpful in supporting the DWI offender to not drink and drive. Usability test participants may not feel comfortable responding to questions about their opinions on appeal, ease of understanding, navigation, and functionality of the *B-SMART* mobile app. There are no anticipated risks from completing the self-report questionnaires. If signs of minor stress or fatigue are apparent, participants will be given time to take a break from completing the questionnaires. For the randomized trial, surveys will be completed online, at the participants own pace.

Participants' responses will not be shared with anyone except project staff. Responses to survey questions will be coded to protect confidentiality. All participants will be allowed to withdraw at any time if they are uncomfortable with the discussions. Although half of the potential participants are involved with the criminal justice system as a result of having a DWI, that involvement is overseen by other entities and is not a part of the research project.

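### The plan says who reports adverse events and when, but not how staff would learn of them; the SAE clock starts at occurrence, and annual reporting has no branch above Grade 1

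*Combined protocol and SAP*

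**What the plan says.** The Data and Safety Monitoring Plan sets the reporting rules. For serious events, "All study staff will be required to report serious adverse events within 24 hours of their occurrence, regardless of their relevance to the study", and then "The PI will be required to provide a report of all serious adverse events to the IRB within 24 hours of the reporting". For the rest, "Only Grade 1 events are expected on this trial. Thus, adverse events will be reported annually, as required by DHHS". Responsibility is assigned: "The PI and Project Coordinator are responsible for reporting all adverse events to the IRBs". On preparation, "Relevant study staff will also be trained in monitoring and documenting adverse events". Investigators also review critical events, a term the plan does not define. There is no independent board, because the trial is judged very low risk.

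Data collection is described elsewhere. Section 3C.6.1 has surveys at baseline, 3 months and 9 months, which "include DWI offender and CFM alcohol frequency and use measures and measures of family communication and functioning", plus one extraction of lockout records at 9 months. Sections 3C.7.2 to 3C.7.4 and 4.3 (Outcome Measures) fill in the content: adapted Form 90 drinking measures, three family instruments, demographics, a usability scale and server-logged app use. On survey mode, section 3.1.B (Potential Risks) says: "For the randomized trial, surveys will be completed online, at the participants own pace".

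**The concern.** Reporting and ascertainment are separate tasks, and only the first is planned. A rule that obliges staff to report is of use only for events they know about. In this trial follow-up is remote, and nothing in the measure lists asks whether someone was hurt, needed hospital care or was distressed by taking part.

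The intervention works through family conversations about drinking. It enrols people on DWI probation, whom section 3.2.B itself regards as more vulnerable for being in the justice system, together with their relatives. The absence of an independent board rests on the judgement that risk is very low. If events are not sought, the trial does little to test that judgement. The two timing rules add to the problem: one sets a deadline that staff often could not meet, and the other treats an expectation about severity as if it settled what to do when the expectation fails.

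**Working it through.** The plan gives no adverse-event figure to reproduce. The check sets the sections side by side, with simple arithmetic on timing.

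**1. How could staff learn of an event after randomization?**
- Reminders to open the app or pamphlet for two weeks, then a telephone call to non-users in either arm (3C.6.3). Stated purpose: to encourage use.
- A hotline run by the media developers (3C.6.3). Stated purpose: technical help.
- Survey reminders by text and email, and mailed or emailed copies for non-responders (recruitment and retention text). Stated purpose: survey completion.
- Surveys at 3 and 9 months: 600 participants x 2 = 1,200 scheduled follow-up surveys, none with a listed adverse-event item.
- Lockout records at month 9, for offenders only.
- After withdrawal, no further data are collected (3.2.A), so harm that leads someone to withdraw may go unrecorded.

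Section 4.3 lists no adverse-event outcome, and the Statistical Analysis Plan contains no safety analysis. No adverse-event definition, seriousness criteria or named grading scale is given.

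**2. Can the staff SAE clock be met?** The longest gap between surveys is 9 - 3 = 6 months, about 183 days, against a limit of one day from occurrence. Suppose the surveys did ask, were answered on schedule, and events fell uniformly over 9 months (all three are assumptions).
- Events in the first 3 months wait 1.5 months on average; events in the last 6 months wait 3.
- Mean lag = (3/9)(1.5) + (6/9)(3) = 0.5 + 2.0 = 2.5 months.
- Share of events within a day before a survey = 2 / 274 days = 0.7%.

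These figures describe the surveys as the sole route. A telephone call or a volunteered report could be quicker, so they show what the surveys could deliver, not what compliance would be. The PI's own clock starts at the staff report and does not have this defect.

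**3. Which rule covers which event?**
- Serious, related or not: 24 hours from occurrence to staff report, then 24 hours to the IRB.
- Non-serious, expected, Grade 1: annual.
- Non-serious and above Grade 1: no separate rule, so the annual one applies by default.
- Non-serious, unexpected and related: the same.

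Annual reporting can mean a wait of up to 12 months. Participation lasts 9 months (section 4.5). An event in the last two groups could therefore reach the IRB after that person's participation has ended.

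**4. What can be compared by arm?** Lockouts (with dates), offender drinking, and family cohesion, conflict, communication and shared activities. From the listed measures, nothing on injury, crash, hospital or emergency care, or distress attributed to the study.

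**The case against.** The strongest reply is that this is an IRB-reviewed trial of an educational app taking at most 120 minutes, and that a light monitoring plan is proportionate. That stands, and it keeps the point modest. Several stronger readings are tempting, and the documents do not support them.

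- *That events have no route to the IRB.* They have one: staff are trained, named people report, and SAEs have deadlines. What is missing is the step before it.
- *That the safety record would be empty whatever happened.* This requires that no event ever reaches staff unprompted. With 9-month SAE risk r and share c of events reaching staff, the chance of no report is (1 - rc)^600. The documents give neither r nor c. Purely as illustration, r = 1% gives 0.74 at c = 5%, 0.30 at c = 20% and 0.05 at c = 50%; r = 5% gives 0.22 at c = 5% and 0.002 at c = 20%. Under-counting is likely; an empty record is not assured.
- *That harm from the app could not be detected.* More lockouts, more drinking or worse family conflict would show in the comparison by arm, although these measures are not linked to safety reporting.
- *That a break when stress is visible is the only protection against distress.* Section 3.2.B also lets participants skip questions and stop at any time, and both work online.
- *That the plan orders annual reporting whatever the grade.* It ties annual reporting to expecting Grade 1 only. The defect is a missing branch.

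Two further cautions stand. The questionnaires are not in the documents, so an adapted instrument might contain a relevant question. Consent and contact pages were removed from the text, so the absence of a contact for reporting problems cannot be assumed. It is also fair to say that a clock from occurrence is stricter than one from awareness. But a deadline that may pass before anyone knows of the event gives no workable control.

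**Conclusion.** The concern holds as a gap in ascertainment with two drafting faults in the reporting rules. Followed as written, the plan would probably under-record harms other than lockouts, drinking and family-scale changes, and could not compare them reliably by arm. The staff SAE deadline cannot be met reliably with up to 6 months between surveys. Non-serious events above Grade 1, and unexpected related ones, have no rule of their own.

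The size of the under-recording cannot be estimated, because the documents give no event rate and no capture rate. The conclusion rests on the measure lists being a complete account of the surveys. The efficacy analysis is not affected. This is a cheap improvement that should be made, not a flaw that undermines the trial.

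**What to change.** 1. Add one short adverse-event item set to the 3- and 9-month surveys of offenders and CFMs, worded identically in both arms: for example injury or crash, hospital or emergency care, and distress attributed to the study. State who reads the answers as they arrive. Any item on arrest or family violence needs confidentiality and response wording agreed with the IRB, given the assurances in sections 3.1.B and 3.2.B that responses stay with project staff and are not available to the courts.
2. Tabulate these items by arm at the final analysis. Tables by arm should not go to the Expert Advisory Board during the trial: it includes investigators (3C.4), and section 3C.9 relies on project staff being blind to condition.
3. Start the staff SAE clock when staff become aware of the event.
4. Limit annual-only reporting to expected Grade 1 events, and send other events by the prompt route the plan already has for SAEs.

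The cost is a few minutes of survey time, revised monitoring-plan wording, an IRB amendment and the handling of some unrelated events. Sample size and the primary analysis do not change.
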